enrollment). TrialFacts, BuildClinical, and other clinical research advertising businesses utilize targeted digital media advertising to recruit participants.

We will also employ additional recruitment methods to research potential study participants. First, we will use ResearchMatch.org to contact potential study volunteers (using IRB approved language) to see if they may be interested and a good fit for this study. We will attempt to search for potential participants near study sites. Second, given the success of cold-contact recruitment used in a current study (Pro105269) and at MUSC generally to reach a wide range of patients that might not otherwise take part in research studies, we propose to use cold contact methods to reach smokers in study location areas. Patient reports will be requested from the MUSC Biomedical Informatics Center [BMIC]). We will ask for searches of the medical record that identify smokers, ages 18-40, within 30-40 miles of Charleston, Pickens, or Florence from MUSC and all regional hospitals. BMIC will gather contact and demographic information (name, phone number, street address, zip code, etc.) for potential study participants, as well as smoking status. All potentially eligible patients will be selected for recruitment unless they have specifically opted out of research communication. Patients' opt-out preferences will be documented in their REDCap Research Contact Form. The study team will not cold contact any patients who already have opt-out preferences noted in their electronic health records.

Additionally, Respondent-Driven Sampling (RDS) will be used to enhance recruitment. The RDS sampling methodology is based on recruiting the eligible friends and acquaintances of each participant so that the sample "snowballs." Each eligible participant who is enrolled into the study, and agrees to take part in this recruitment assistance, is eligible to receive compensation for successful referrals. A referral will be instructed to call the study team to be screened for eligibility. If that person successfully enrolls into the study (i.e., completes the Day 0 visit and begins taking study medication), the participant who referred them can receive \$30 in compensation for each eligible participant that is referred and enrolled in the study. The research team has used these methods successfully in the past.

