Additionally, Respondent-Driven Sampling (RDS) will be used to enhance recruitment. The RDS sampling methodology is based on recruiting the eligible friends and acquaintances of each participant so that the sample “snowballs.” Each eligible participant who is enrolled into the study, and agrees to take part in this recruitment assistance, is eligible to receive compensation for successful referrals. A referral will be instructed to call the study team to be screened for eligibility. If that person successfully enrolls into the study (i.e., completes the Day 0 visit and begins taking study medication), the participant who referred them can receive \$30 in compensation for each eligible participant that is referred and enrolled in the study. The research team has used these methods successfully in the past.

In addition to compensation described above, participants enrolled in the EMA supplement portion of the study will be compensated contingent on completion of EMA surveys. For each 1-week burst of EMA data collection, participants may earn a maximum of \$70 for completion of sessions on a sliding scale. A maximum of \$280 can be earned over the four, 1-week bursts of EMA data collection.

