10.0 Statistical Analysis and Data Management

Analytic Strategy.

Power and sample size. The proposed study is powered to detect a meaningful difference in end of treatment tobacco abstinence between cannabis co-users and tobacco only users. Secondarily, the study will assess the relationship between cannabis use patterns during treatment and nicotine dependence severity in co-users. Specific Aim #1: Examine the impact of cannabis co-use on tobacco cessation outcomes among co-users compared to tobacco only users. Hypothesis 1: Co-users will have lower rates of 7-day point prevalence abstinence from tobacco at the end of treatment (Week 12) compared to tobacco only users. In a cross-sectional survey of national household data (51), tobacco cessation was reported among 65.5% of respondents who endorsed no cannabis use as compared to 21.8% of tobacco cessation in those reporting current cannabis use ($\Delta=43\%$). Studies examining the efficacy of varenicline for tobacco cessation (108, 109) noted near 50%-point prevalence abstinence at treatment conclusion (Week 12) in the varenicline-treated group. Finally, in our recently completed adolescent varenicline trial (U01 DA0317779), youth cannabis co-users reported point prevalence tobacco abstinence in 20% of participants at Week 12 and 43% in those who use tobacco only (analysis with all available data). The proposed R01 study intends to apply a successful tobacco treatment (varenicline) paired with contingency management in treatment-seeking smokers. Assuming a similar abstinence rate in tobacco only users (45%) and a successful abstinence rate in participants who are cannabis co-users as compared to the adolescent study (20%; $\Delta=25\%$), to achieve 80% power with a 5% type 1 error rate, a sample of 82 participants in the cannabis co-using cohort and 41 in the tobacco only cohort. However, to account for the inclusion of 2 study sites in the design, an additional fixed factor of site will be included in the analytic models. Although we hope that equal proportions of co-users and non co-users present at each site, we understand that the fundamental differences between the Charleston metro area, Pickens County SC, and Florence exist and may cause some correlation between co-use group and study site. Assuming that the proportion of variance in co-use groups due to study site and other covariates may be moderate ($R^2=0.25$) and that attrition will not exceed 25%, we have adjusted our study sample size to account for this scenario. This increases our randomized sample to a total of 208 (139 cannabis co-users and 69 tobacco only users) accounting for both site correlations with co-use group and anticipated attrition. If site correlations with study outcomes or attrition are lower than pre-specified, our statistical power will exceed 80%. Specific Aim #2: Among co-users, assess changes in cannabis use during tobacco cessation treatment. Hypothesis 2: Co-users with moderate to high severity of nicotine dependence will demonstrate increases in concurrent cannabis use, while lower severity of nicotine dependence will yield no changes in cannabis use. To attain adequate power to assess Aim #2, a within co-use cohort comparison, the study will oversample the cannabis co-use cohort as compared to the tobacco only cohort (2:1). At screening, nicotine dependence will be assessed via the Fagerström Test for Nicotine Dependence (FTND) (92) and categorized accordingly: low nicotine dependence (0-4), medium or high nicotine dependence (5-6; 7-10). Cannabis use during the final 4 weeks of study treatment as compared to baseline use will be assessed among co-users. Based on our preliminary data from an ongoing adult tobacco cessation trial (R34 DA042228), we have nearly equivalent numbers of participants falling into low and moderate/high nicotine dependence categorizations (Mean=4.5; Median=5). Therefore, we anticipate ~40% will have medium/high nicotine dependence. With 208 participants, 139 in the cannabis co-use cohort (104 completers), we will achieve 80% power with a type 1 error rate of 5% to detect a between group cannabis use difference of Cohen's $d\approx0.6$ (Med/High nicotine dependence vs. low nicotine dependence).

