Primary Study Aims: Aim 1: To assess the difference in the log-odds of abstinence from tobacco at the end of treatment (Week 12) between baseline cannabis co-users compared to tobacco only participants, augmented inverse probability weighted logistic regression models will be developed. The inverse of the conditional probability of being in the cannabis co-use cohort will be included in the model to account for inherent imbalances between study groups and to reduce bias by resembling a randomized controlled trial. In addition to the inverse propensity weights, AIPW methods incorporate a covariate and study site adjusted model for the study group outcome (114). Aim 2: To assess the association of baseline nicotine dependence severity (Med/High nicotine dependence vs. low nicotine dependence) with cannabis use rates during study treatment, generalized linear mixed effects models will be assessed with cannabis use rates and amounts during the final 4 weeks of treatment as the primary indicator of cannabis use severity and nicotine dependence group as the primary model predictor. In addition to grouping by nicotine dependence severity, continuous levels of dependence severity (FTND score) will be modeled to assess possible linear and quadratic relationships between dependence severity and cannabis use. Following examination of the differences in end of treatment cannabis use rates based on baseline nicotine dependence, rates of cannabis use will be assessed by group (nicotine dependence severity) over all weekly study visits to determine if those with increased dependence severity exhibit a different trajectory (slope and pattern) of cannabis use during the entire study treatment. Model-based means and associated standard errors will be used to test group level differences. Exploratory Aim: To assess the relationship between baseline cannabis use severity and tobacco outcomes, generalized linear mixed effects models will be developed with weekly 7-day point prevalence abstinence from tobacco as the primary model outcome. In addition to tobacco abstinence, weekly average cigarettes per day will be examined as an indicator of use reduction differences over time. Longitudinal patterns in tobacco abstinence and use amounts will be modeled through the inclusion of baseline cannabis use severity indicators, study visit, and baseline tobacco use rates as model covariates. Additionally, differential effects over time will be examined with the inclusion of the interaction of cannabis use severity and study visit. Model-based means and associated standard errors will be used to test group level differences across the study treatment.

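### Paid referral of friends links some participants, but the plan does not say how the Aim 1 standard error allows for those links

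*Combined protocol and SAP*

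**What the plan says.** Section 7.0 (Recruitment Methods) lists many channels: print, broadcast and digital advertising, clinic referral, college postings, recruitment vendors, a volunteer registry and cold contact from medical records. It then adds respondent-driven sampling, described as follows: "The RDS sampling methodology is based on recruiting the eligible friends and acquaintances of each participant". A participant who agrees to help receives $30 "in compensation for each eligible participant that is referred and enrolled in the study". No limit on referrals per participant is stated. Section 9.0 (Participant Compensation) repeats this: "Additionally, Respondent-Driven Sampling (RDS) will be used to enhance recruitment".

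Section 10.0 sets out the analysis. For Aim 1, "augmented inverse probability weighted logistic regression models will be developed", with a covariate- and site-adjusted outcome model. The propensity variables include social influences, education, motivation to quit and nicotine dependence. Generalized estimating equations (GEE) are specified for weekly abstinence, which is correlation over time within a person. For sample size, the plan gives "a sample of 82 participants in the cannabis co-using cohort and 41 in the tobacco only cohort", then inflates to 208 for site and covariate correlation with co-use (R² = 0.25) and 25% attrition. Referral chains, a design effect and a cluster-robust variance are not mentioned anywhere in Section 10.0.

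**The concern.** Friends who enter the same cessation study may resemble each other in cannabis use and may affect each other's quit attempts. When both the exposure and the outcome are alike within a chain, the chain carries less information than the same number of unrelated people. A standard error that ignores this is then too small, and the 5% test of the co-use difference rejects too often under the null.

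Two features of the protocol make the mechanism plausible. Section 7.0 expects a later phase in which only co-users are still needed, so a co-user's referral enrolled in that phase would also be a co-user. Section 9.0 makes enlisting social support part of the counseling. Neither feature shows that the correlation exists or how large it is.

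The planned site factor and covariates, including social influences, remove only the similarity they explain. GEE for weekly data does not address links between people unless the cluster is defined as the chain.

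**Working it through.** **1. The plan's own figure.** Inputs from Section 10.0: abstinence 45% (tobacco only) against 20% (co-users), allocation 1:2, 80% power, 5% type I error (taken as two-sided).

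- Unpooled variance: (1.96 + 0.8416)² × (0.45×0.55 + 0.20×0.80/2) / 0.25² = 7.849 × 0.3275 / 0.0625 = 41.1 tobacco only, matching the stated 41 and 82.
- Pooled variance: 39.1 tobacco only, total 117.3. Then 117.3 / 0.75 / 0.75 = 208.5, matching the stated 208.
- Working back: 208 × 0.75 × 0.75 = 117 effective participants. Power with 139 and 69 enrolled is 79.8%.

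The sample size therefore has almost no spare margin, and neither inflation factor is a referral design effect.

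**2. Design effect under assumed chains.** The documents give no chain size *m* or intra-chain correlation (ICC), so the values below are assumptions. They take every chain as sharing co-use status, and the ICC is what remains after covariate and site adjustment.

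- DE = 1 + (m − 1) × ICC
- Type I error of the uncorrected test = 2 × P(Z > 1.96/√DE)
- Power of the uncorrected test = P(Z > (1.96 − 2.80)/√DE)
- Power with the corrected standard error = P(Z > 1.96 − 2.80/√DE)

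| Mean chain, ICC | DE | True SE / naive SE | Type I error, uncorrected | Power, uncorrected | Power, corrected SE | N to restore power (208 × DE) |
|---|---|---|---|---|---|---|
| 2, 0.05 | 1.05 | 1.025 | 5.6% | about 79% | about 78% | 219 |
| 3, 0.10 | 1.20 | 1.095 | 7.4% | about 78% | about 72% | 250 |

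The type I error and the corrected-SE power belong to different tests. Ignoring clustering inflates the type I error and costs little apparent power. Correcting the standard error restores the type I error and shows the power really available.

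**3. Referral as a minor channel.** If 20% of the sample is in pairs, the participant-weighted mean cluster size is 0.8×1 + 0.2×2 = 1.2. With ICC 0.10, DE = 1.02 and type I error is 5.2%. With ICC 0.20, DE = 1.04 and it is 5.5%.

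A simulation of 156 completers (208 × 0.75) used an unadjusted two-proportion test and 6,000 repetitions per setting. With 20% in pairs sharing co-use status, it gave a type I error of 5.3-5.5% and a true-to-naive SE ratio of 1.01-1.02. Its Monte Carlo error is √(0.05×0.95/6000) = 0.3 points, and runs with no clustering gave 4.7-5.5%. The pair scenario is therefore barely distinguishable from nominal.

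With latent outcome correlation 0.3, 40% of the sample in trios gave 6.5%, and 60% in groups of four gave 8.7%.

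**4. Direction.** With co-use independent within chains, the same simulation gave 4.8-5.5%, which is no material inflation. Where linked people fall in different groups, Var(p₁ − p₀) = V₁ + V₀ − 2Cov. A positive covariance then lowers the true variance, so the naive standard error is too large.

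**The case against.** The strongest objection is that the effect is probably small. Referral is opt-in and comes after a long list of other channels. It counts only when the friend meets all entry criteria, completes Day 0 and starts medication. If few participants arrive this way, the standard error changes by one or two percent. This stands, and it makes the point a low-cost safeguard and not a threat to the trial.

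A second objection is that only correlation remaining after adjustment matters, and the planned adjustment includes social influences and site. This stands in part: adjustment lowers the residual correlation but is not a variance correction.

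A reader might also infer that every planned analysis assumes independent participants. The documents do not say so. They leave the variance estimator for the primary model and the random effects of the mixed models unspecified, so what can be said is that the handling of referral links is not stated. Likewise, uncapped referral is only the absence of a stated cap.

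Finally, since paying a referrer requires knowing who referred whom, the chains could perhaps be rebuilt later. That is likely, but the documents do not say that the link will be kept in the analysis data.

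**Conclusion.** The gap is real and minor. The plan recruits partly through acquaintances, and no analysis or sample-size step in Section 10.0 accounts for correlation between linked participants.

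The Aim 1 standard error would be too small only if linked participants share both co-use status and residual outcome. That is plausible but not shown. For modest referral, type I error stays near 5.3-5.5%. It reaches 5.6% to 7.4% only if chains averaging two or three, with ICC 0.05 or 0.10, run through the whole sample.

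A reader might infer a severe problem from a case such as mean chain 5 with ICC 0.20 (DE 1.8, uncorrected type I error 14%, corrected power about 55%). That case needs long, strongly correlated chains sharing co-use status across the entire sample, which does not fit one opt-in channel among many. The uncorrected test would also still have about 73% power there, so the 14% and the 55% do not describe the same analysis.

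**What to change.** Keep the referrer's study ID as an analysis field and define referral chains from it, with non-referred participants as single-member clusters. State in Section 10.0 that standard errors for Aim 1 and the longitudinal models will use a cluster-robust estimator by chain, or a bootstrap that resamples whole chains and refits both the propensity and outcome models. Prespecify this at least as a sensitivity analysis. In the GEE models, the chain and not the person would be the cluster. Report the number and size of chains and the share of participants who came by referral.

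The cost is one or two sentences in the plan and one data field that payment already appears to require. Intervals widen if positive clustering is present: by about 2.5% at DE 1.05 and 10% at DE 1.20, and hardly at all if referral is a minor channel.

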8.0 Consent Process

Prior to the initiation of any study procedures, written informed consent and HIPAA authorization will be obtained by the designated research staff. The informed consent process will include a thorough discussion of potential risks associated with participation, including potential adverse effects of study medication.

Potential participants will be given a copy of the IRB-approved consent form and asked to read the document with ample opportunity to take their time in its review. The participant will have the consent documents reviewed with delegated study personnel and have all questions and concerns addressed to their satisfaction. Anyone who cannot demonstrate appropriate understanding of the study or who expresses an unwillingness to participate in the protocol will be ineligible to participate and will be assisted in finding treatment resources. Those who demonstrate understanding of the study and voluntarily agree to participate will be asked to sign the informed consent form and proceed with the screening assessments. As part of the informed consent procedures, participants will be asked to provide or decline consent to be contacted for future studies. Copies of the signed consent documents will be given to the participants for their reference and resource.

We may also use several different methods to complete electronic informed consent, if applicable, that include the following: 1) via MUSC's doxy.me system (teleconsent), or 2) via REDCap electronic consent (e-consent) combined with a video discussion (doxy.me). As a last resort, we will also email the consent document to the participant and conduct the informed consent via video chat (doxy.me). Participants can then email or mail the signed consent back to the research team. Video chat functionality will only be used if all parties have the availability.

All doxy.me signed consent forms will be saved as PDF files within our study records. E-consent via REDCap will be saved with a separate informed consent database. This database will not include any data collected as part of the trial. Using these systems, signatures on the consent form may be obtained electronically via REDCap/doxy.me. In the case that participants mail back hard copies of the consent (in rare instances), those will be stored in locked file cabinets in the offices of research staff. Participants will also be asked to complete a W-9 during the informed consent/e-consent process.

To manage participant bias, the title of the study details in the informed consent document are not as specific as they would normally be to maintain the integrity of this research.

A waiver of consent will be obtained for quality improvement saliva samples. These results will be not used for research purposes.

9.0 Study Design / Methods

Screening Visit: Interested individuals will receive a telephone screening to determine if they may be eligible. They will then be scheduled for a screening visit, consisting of informed consent, followed by a medical history and physical exam by a study clinician, self-report questionnaires, and semi-structured interviews to determine eligibility. If an individual is a patient at MUSC, our medical clinician will have access to his or her medical record and will check for current health issues or medications that may affect safety. At this visit, participants will also see an example mobile diary (on their own mobile device or a loaner smartphone) and complete it in office. Participants will then begin to receive daily diaries, which they will complete every morning to report on their cigarettes smoked, other tobacco use, other drug use, and alcohol used during the previous day. Participants will complete these morning reports daily through their week 12 visit. For those who are eligible, we will employ a training visit separating screening and the start of medication (Day 0) to ensure adequate compliance before the 12-week treatment begins. At this training visit, participants will see an example medication video (on their own mobile device or a loaner smartphone) and complete it in office. After the training visit, participants will begin receiving daily example medication videos, which they will be instructed to complete twice a day to prepare for Day 0. This period constitutes a pre-quit monitoring lead-in prior to the dispensation of medication. The study design is shown in Figure 4.

[figure not shown]

Figure 4.

used during the previous day. Participants will complete these morning reports daily through their week 12 visit. For those who are eligible, we will employ a training visit separating screening and the start of medication (Day 0) to ensure adequate compliance before the 12-week treatment begins. At this training visit, participants will see an example medication video (on their own mobile device or a loaner smartphone) and complete it in office. After the training visit, participants will begin receiving daily example medication videos, which they will be instructed to complete twice a day to prepare for Day 0. This period constitutes a pre-quit monitoring lead-in prior to the dispensation of medication. The study design is shown in Figure 4.

Training Visit: At this training visit, participants will see an example medication video (on their own mobile device or a loaner smartphone) and complete it in office. After the training visit, participants will begin receiving daily medication videos, which they will be instructed to complete twice a day so as to prepare for Day 0. Participants will complete these medication videos twice a day through their week 12. This period constitutes a pre-quit monitoring lead-in prior to the dispensation of medication. Participants will receive a brief counseling session in preparation for their target quit date (Day 8).

Day 0: On Day 0, participants will be given their first week of varenicline. The standard dose titration schedule will be used, which includes 0.5 mg once per day (q.d.) on Days 1-3, 0.5 mg twice per day (b.i.d.) on Days 4-7, and 1.0 mg b.i.d. starting on Day 8. Dosing of 2.0 mg per day will be maintained for the next 11 weeks. They will be given contact information if they are experiencing adverse events, including an emergency number for after-hour issues with medication. Participants will be encouraged to contact study personnel at any time to address concerns. The medical clinician/Co-I will provide medical supervision for this study and designated medical clinicians will provide oversight for any adverse events. MUSC medical clinician(s) will have the ability to support non-Charleston based site staff with adverse events and other medical concerns remote via telephone, doxy.me, or other HIPAA-compliant, MUSC-IS approved platforms for telehealth. If a participant experiences intolerable medication-related adverse events, a dose reduction to 0.5 mg twice per day may be undertaken (temporary or permanent dose reduction depending on alleviation of symptoms). If the participant is unable to tolerate the reduced dose, the medication will be discontinued, and the participant will continue to be tracked. At this visit, participants will be reminded or retrained on how to upload videos of themselves taking their medication (twice daily) via REDCap. Medication to be used by non-Charleston study sites will be ordered through MUSC and shipped directly to research staff or directly to the participant's home via registered courier. Staff will store medication in a controlled access environment and only accessed by designated staff.

Behavioral strategies will also be used to promote tobacco abstinence. First, psychosocial counseling will be administered at the training visit and Day 0 in preparation for the target quit date (Day 8). During the treatment phase, brief counseling (<5-10 minute) will be provided at all weekly visits by trained research staff and will include motivational enhancement for medication adherence and tobacco cessation. The content of counseling will be skills-based and focused on enlisting social support, recognizing smoking triggers, managing craving/withdrawal/stress, etc. Cannabis use will not be addressed as part of counseling. If the participant expresses a desire to reduce/quit using cannabis, standard information and resources will be provided, but this will be kept minimal to avoid researcher-imposed impact on cannabis use. Participants will be encouraged to pursue desired cessation, but will be reminded that the current study is focused on tobacco cessation.

Mobile sessions: Each morning during the 12-week study (and one week leading up to Day 0), participants will receive a text message and email link to complete their daily diary. Daily diaries will be administered and data will be managed through the Research Electronic Data Capture system (REDCap) (82). Our research team has previously used daily diaries through REDCap (77). Standard questions will be administered regarding substance use that occurred during the prior day (midnight to midnight of the past calendar day).

Weekly Visits (Weeks 1 - 12): Participants will be asked to complete weekly visits for the next 11 weeks. During visits, research staff will review compliance with daily diaries and discuss medication adherence over the past week (assessed through REDCap medication videos, smart bottle caps, daily diaries, and pill counts). Medication tolerability will be systematically assessed, and medical clinicians will be contacted if any potentially related adverse events are reported. Self-report assessments will be administered (e.g., craving, withdrawal, etc.). Brief cessation counseling will be conducted and bonus compensation (i.e.,

contingency management) will be provided based on tobacco abstinence. Vitals will be obtained at weeks 4, 8, 12, or as needed throughout the study (any visit). Urine samples will be collected and separated for: 1) immediate tests conducted by research staff (cotinine, cannabinoids, pregnancy [weeks 4, 8, 12, or as needed], other drugs); and 2) delivery to the MUSC Charleston laboratory for quantitative urinary cotinine and cannabinoid (creatinine-normalized) assay runs. Staff will label and store urine samples (if not in Charleston) to be shipped to MUSC per laboratory protocols. A sub-sample of 10 participants who are cannabis co-users will also be asked to participate in a study addendum that includes the collection of a saliva sample to test for various cannabinoids. Participants will complete their end-of-treatment study visit (Week 12), and a follow-up visit at Week 26. Early termination (ET) visits (in-person or remote) may occur if a participant wishes to withdraw from the study. Week 12 assessments and procedures will be conducted for ET visits, should they occur.

Follow-up Phone Visit (Week 16): During this follow-up visit, participants will be contacted for a brief phone call to assess overall health, as well as current tobacco and cannabis use.

Follow-Up Visit (Week 26): During this final follow-up visit participants will complete self-report questionnaires (e.g., craving, withdrawal, etc.). Daily use of cigarettes, other substances, alcohol, and other tobacco will be gathered during the follow-up period.

Unscheduled Visit (PRN): Participants may be asked to return to the study office for unexpected incidental needs such as addressing a technological concern with the loaned study equipment (phone) or any other issue that cannot be resolved remotely. It is not anticipated that any supplemental data would be collected at these visits and they should take less than 15 minutes to complete.

If a participant has an unexpected conflict with attending a visit or the visit must be completed by staff remotely (e.g., transportation issue or travel), arrangements (i.e., phone visit) may be made to remotely complete visit procedures, in order to maintain data collection and study engagement. There is the potential, with proper planning, that participants may be able to complete urine needs at home. Participants will be given proper materials and properly instructed on how to collect/store urine while at home.

Remote Visits: All procedures that can be conducted remotely or through minimized participant contact are possible and will be used as needed (i.e., phone visits, online REDCap surveys, remote consent, detailed medical histories through telehealth platforms). When in-person contact is needed, steps will be taken to minimize contact or the need for a participant to enter a shared research suite (i.e., returning medication bottles in the parking lot, breath CO in their car, at home urine collection procedures, etc.) to comply with any MUSC restrictions in place at that time. At home urine procedures may be conducted (instant-read cotinine, urine drug screen and pregnancy tests), in addition to freezing and returning samples at a later time for laboratory assays (based on supply availability, participant or staff comfort with at home procedures, etc.). If occurring at Day 0, a pregnancy test will be completed prior to medication administration. Participants will be given proper instructions on how to complete the test, and all testing procedures will be performed in real time with participants via video conference (i.e., Zoom, Doxy.me, etc.). Study staff will confirm instant-read cotinine results over video.

Most study procedures can be done remotely, and this will be utilized at the Florence site. Staffing at that site will be minimal and most procedures will be conducted by Charleston or Pickens staff approved and trained on study procedures. Florence staff will engage in human subjects research, data and specimen collection, etc. and will be trained and approved on this study.

Research staff may arrange for taxis to transport participants to research offices when personal transportation is not possible. In rare circumstances, when taxis are not possible, research staff may meet

participants in the community at a public location in order to exchange study supplies (e.g., at home urine samples, medication bottles, or provide study supplies to participants). Safety procedures will be followed if this option is deemed necessary.

EMA Supplement

Procedures: In addition to procedures described above, tobacco-cannabis co-using participants (N=48) will be asked to complete 1-week bursts of EMA data collection at four timepoints during the study:

[figure not shown]
1) baseline/pre-medication (to occur between screening and the Day 0 visit where medication is dispensed), 2) Week 1 (starting at the target quit date and going until Week 2), 3) Week 11 (starting at Week 11 and ending at the Week 12 end-of-treatment visit, and 4) Week 25 (starting at Week 25 and ending at the Week 26 final follow-up visit; see Figure below). The timeframes listed are ideal. The bursts can shift if there are issues such as technology issues or the participant is difficult to contact. The EMA protocol is part of an NIH-funded EMA supplement to the parent study and will be implemented via the ilumivu mEMA platform, which is compatible with Android and iOS devices. During each 1-week EMA burst during the parent study, participants will be asked to complete four semi-random surveys over a 16-hour period (separated into 4-hour time blocks, 1 session randomly prompted in each block).

Instruments and measures: A complete listing of specific instruments/measures is shown below in Table 2 (Assessment Timeline). Cannabis-related instruments will only be administered among co-users.

Screening/Diagnostic Assessments: Detailed demographic information will be collected at screening, which is necessary to inform the propensity score analysis methods. Locator information will be collected and updated throughout the study. Medical and psychiatric assessments will be conducted by designated medical clinicians and trained research staff to ensure eligibility criteria are met.

Biochemical Verification of Tobacco, Cannabis, and Other Substances: At each study visit, a urine sample will be collected and an instant-read urine drug screen will be conducted, which includes a qualitative urinary cannabinoid test (cut-off of 50 ng/ml) to determine cannabis use status, as well as assays for other commonly used substances (amphetamines, opioids, etc.). Urinary cotinine (a metabolite of nicotine) will be the primary indicator of tobacco abstinence (83). Qualitative urinary cotinine will be tested via instant-read, immunoassay test strips for purposes of contingency management. Urine samples will be aliquoted and delivered to the laboratory for determination of quantitative cotinine levels. Abstinence criteria for quantitative cotinine will be set at 80 ng/ml. Urinary quantitative cannabinoid values (11-nor-9-carboxy- Δ 9-tetrahydrocannabinol; THCCOOH) will be tested at MUSC. Urine creatinine will also be obtained, to allow for creatinine-normalized urine cannabinoid levels. Saliva samples will be collected for 10 study participants at one time point. A saliva sample may be collected in addition to other biochemical measures for quality improvement purposes and will not be used for research purposes.

Substance Use Assessments: Several substance use assessments will be conducted throughout the study, including; detailed use history (for all substances), dependence level, motivation to quit (tobacco and cannabis), craving, withdrawal, satisfaction and subjective effects (cannabis and tobacco), and motives for use (full listing in Table 2). TLFB procedures (84) will be used at screening (30-day calendar) to assess the frequency and quantity of tobacco use (cigarettes per day and other tobacco use), cannabis, alcohol and other drug use. In order to determine an individual-specific cannabis unit, cannabis quantification procedures will be conducted at screening and as needed when new methods of cannabis use are endorsed. For plant material-based methods, grams of cannabis will be estimated using a surrogate substance (78).

Participants are asked to show research staff the average amount of cannabis that they use (with the surrogate) for each combustible modality endorsed (e.g., joints, blunts) and report the estimated dollar amount associated with that quantity. The surrogate substance is then weighed on a scale to determine average grams per method. That amount then serves as the individual's standard unit (e.g., "standard blunt") for future reporting. This quantification procedure has been successfully implemented previously (85, 86), is being used in an ongoing study at MUSC (R01 DA038700), and has been shown by our team to improve the predictive validity of clinical outcomes (87). The gram estimation procedure will not work for non-plant based cannabis use methods, which are challenging to quantify. We will quantify these non-combustible methods with techniques used in an ongoing study (R01 DA038700). We will assess times used or hits taken (waxes, dabs, concentrates, lotions), milligrams ingested (edibles, drinks), and milliliters used (oils, tinctures, liquids). We expect that non-combustible methods will continue to evolve and we will modify our procedures accordingly.

Safety Assessments and Medication Adherence: Adverse events will be systematically collected at all visits and will be coded in Medical Dictionary for Regulatory Activities (MedDRA) terms. Medication adherence will be monitored through several methods; pill counts, smart bottle caps, daily self-report of doses taken through the daily diaries, and review of medication videos submitted through REDCap.

EMA measures: EMA items will include 10-30 items assessing cannabis use, tobacco use, and cannabis-tobacco co-use and relevant variables related to co-use relationships. At each EMA session signal, participants will be asked to report whether they have used cannabis, tobacco, or both substances since the previous assessment. Branching logic will be used to administer follow-up items on quantity and frequency of use since the previous assessment, subjective effects, cannabis intoxication, tobacco craving, etc. Each assessment is expected take 1-3 minutes to complete.

Table 2. Assessment Schedule

Study Week →	SC	T	Treatment Phase												F/U	
	M	1	2	3	4	5	6	7	8	9	10	11	12	16	26	
Informed Consent/Demographics	X															
Locator Form and Updates	X	X	X	X	X	X	X	X	X	X	X	X	X	X	X	X
Medical/Psychiatric Assessments																
Medical History and Physical Exam	X															
